5.4 CONCOMITANT TREATMENT

A concomitant medication is defined as any prescription or over-the-counter preparation including vitamins. For all patients all administered concomitant medications and therapies, from signing of the informed consent until 30 days after the last dose of study drug must be reported in the designated electronic case report form (eCRF). Concomitant medications required for the study and used

Helsinki University Hospital Comprehensive Cancer Center Hematology
Clinical study protocol NMSG#24/15
prophylactically will be described in the eCRF. Blood products must be reported
on the appropriate eCRF.

5.4.1 REQUIRED CONCOMINANT MEDICATION

These should be initiated at least 24 hours before the first administration of carfilzomib.

Antiviral and pneumocystis jirovecii prophylaxis

Valacyclovir 500 mg po daily or an equivalent acyclovir is a required medication and should be continued for the duration of study treatment. Due to continuous dexamethasone combined with elotuzumab pneumocystis jirovecii pneumonia prophylaxis is recommended according to institutional practice.

Gastrointestinal prophylaxis

Oral proton-pump inhibitor according to institutional practice is required to prevent peptic ulcer throughout the study due to dexamethasone long-term use.

Pregnancy and contraception

Females of childbearing potential must use one effective method of contraception and their partners condom during the study and for 120 days following the last study drug treatment dose and male subjects who are sexually active with FCBP must agree to use condom during the study and for 180 days following the last study drug treatment dose. If a menstrual period in a FCBP does not occur at the anticipated time, study drug treatment must be interrupted, and a serum pregnancy test must be performed. Study drug administration may resume after documentation of negative pregnancy test.

5.4.2 OPTIONAL AND ALLOWED CONCOMITANT MEDICATIONS

Allopurinol or other approved uric acid-lowering agent is allowed to use in patients with high risk of tumor lysis syndrome due to high tumor burden. Adequate hydration must be given to reduce the risk of tumor lysis and renal impairment with these patients. Mycostatin and oral fluconazole may be used at the investigator's decision. Antiemetics and antidiarrheal drugs are recommended

Helsinki University Hospital Comprehensive Cancer Center Hematology
Clinical study protocol NMSG#24/15

to use as necessary. Granulocyte growth factors are allowed to use in neutropenia in accordance with ASCO Guidelines, but those are not allowed to give prophylactically. Red cell and/or platelet transfusions and erythropoietin are allowed to use according to institutional guidelines if clinically needed and patients can have bisphosphonates by recommended guidelines.

5.4.3 PROHIBITED AND/OR RESTRICTED TREATMENTS

Other antimyeloma treatment than study protocol treatment during the study is not allowed. Glucocorticoids are allowed to use for nonmalignant situation like asthma with a dose of no more than ≤ 4 mg/day dexamethasone or prednisone ≤ 20 mg/day. Need of plasmapheresis indicates myeloma progression and the patient will end the study treatment.

5.5 STUDY DRUG ASSIGNING

This is open-label study without any randomization or stratification. All patients will have same study treatment protocol. The responses will be analysed additionally based on stratification by del17p, t(4;14), +1q and also by ISS stage.

5.5.1 STUDY DRUG PACKAGING AND LABELING AND ORDERING

Carfilzomib

Study drug carfilzomib will be delivered free of charge from Amgen covered with final study label on packages based on subscriptions of each study site. Study sites will fill drug medication diary during protocol treatment to document the doses.

Elotuzumab

Study drug elotuzumab will be delivered free of charge from BMS covered with final study label on packages based on subscriptions of each study site. Study sites will fill drug medication diary during protocol treatment to document the doses.

Amgen and BMS will supply study drugs free of charge for the duration of this trial and dosage will be administered by the study protocol. The drugs will be sent

Helsinki University Hospital Comprehensive Cancer Center Hematology
Clinical study protocol NMSG#24/15
as labelled for study drugs to each study site. No distribution will take place
before required documentation is in place.

Dexamethasone

Dexamethasone 40 mg will be taken orally and intravenously by the specified premedication. Oral dose will be taken with the morning breakfast. This drug will be reimbursed as routine medication. Patients will fill drug medication diary during protocol treatment to document their doses.

6. STUDY ASSESSMENTS AND PROCEDURES

Study investigations will be done by the sample flowchart Table 1.

6.1. Medical previous history

- complete medical history
- symptoms of illness
- history of thrombosis of the patient and the relatives
- history of any other malignancies of the patient and relatives
- performance status (ECOG)
- infections
- bone symptoms
- bleeding
- polyneuropathy
- gastrointestinal symptoms

6.2 Physical examinations

- standard physical examination with cardiovascular and neurological (polyneuropathy, autonomic neuropathy) examinations
- orthostatic hypotension

Helsinki University Hospital Comprehensive Cancer Center Hematology
Clinical study protocol NMSG#24/15

- body weight and height, surface area
- exclusion of infections and bleedings

6.3 Hematology

- hemoglobin, hematocrit, leukocytes, leukocyte differential count, neutrophils, platelets

6.4 Blood chemistry

- creatinine, creatinine clearance (Cockcroft-Gault equation)
- liver enzymes (ALAT, AFOS, BIL)
- plasma albumin (ISS)
- serum beta-2-microglobulin (ISS, Appendix 4)
- LD
- CRP
- Ionized calcium, sodium, potassium, phosphate
- Uric acid
- E-Coombs (direct antiglobulin test, DAT) at screening and repeated if clinically unexpected anemia appears

Blood, bone marrow, and urine samples will be required at study entry and at key time-points during the treatment for biochemical, and immunophenotypic assessments, as part of scientific studies in order to monitor MRD as defined by paraprotein, serum free light chain and flow cytometry to define depth and quality of responses. In addition, cytogenetic FISH findings are utilized as prognostic and stratification markers.

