TTNT	Time to next treatment
UK	United Kingdom
ULN	upper limit of the normal range
US	United States
VGPR	Very good partial remission
VTE	Venous thromboembolism
WBC	white blood cell
WHO	World Health Organization

[figure not shown]
Helsinki University Hospital Comprehensive Cancer Center Hematology
Clinical study protocol NMSG#24/15

Table 1. Schedule of study investigations

	Screening	Cycles 1- until end of study, D1 (lab within 5 days before)	Cycles 1-8, D8 D15, D22* (lab within 3 days)	Cycles 1-8 D15	Cycles 9-, D15 until end of study (lab in 3days)	End of study
Medical history	X					
Physical examination + neurool.evaluation	X	X	X**			X
Vital signs	X	X	X*		X	X
Hematology	X	X				X
Immunochemistry	X	X				X
Blood chemistry	X	X				X
Pvk+neut+tromb, K,Na,krea,alat, afos,bil (safety lab*)			X*		X	
Safety assessment, AEs	X	X	X*		X	X
BM aspiration+ 8-color EuroFlow	X		X (when VGPR has achieved, repeated if VGPR/CR and after 1 year if VGPR/CR)			
Bm-MM-FISH	X					
Bone imaging	X					
ECG (a)	X					
Thorax x-ray	X					
Cardiac ECHO	X					
Biobank	X			In CR and at relapse		
Samples to FIMM in Finland	Finland			Bm + blood at relapse		
Pregnancy test (b)	X	X (b)				
Quality of Life		X		X		X

a) ECG in C1-2, D1, thereafter if clinically needed. b) Pregnancy testing must be performed at the beginning of each 28-day cycle and at the end of study visit, applying to women of childbearing potential. * Vital signs not needed on D22 and after C2 Safety lab and AEs on D22 if clinically needed. ** Physical examination if needed due to clinical symptoms.

Table 2. Study schema

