1.4.1.1 Clinical safety and drug-related adverse events

Adverse events in elotuzumab (E) plus bortezomib (B) plus dexamethasone (d) study

Regarding present study with 2nd generation proteasome inhibitor (PI) CFZ combined with ELO and Dex, the most frequently reported AEs when elotuzumab has combined with 1st generation PI, BZM, and Dex were following:

Non-hematology Grade 3-4 events ($\geq 5\%$) in the E-Bd group were diarrhea (8%), pneumonia (6.7%), hyperglycemia (12%), hypokalemia (5.3%), and peripheral neuropathy (8%). In the Bd group, the most frequently reported non-hematology Grade 3-4 events ($\geq 5\%$) were pneumonia (6.7%), hyperglycemia (5.3%), peripheral neuropathy (9.3%), and paraesthesia (5.3%). Grade 3-4 AEs of infection were reported in 17.3% of the E-Bd and 13.3% of the Bd subjects. The most common Grade 3-4 AE of infection was pneumonia, (6.7% for both the E-Bd and Bd groups).

The most common Grade 3-4 SAE was pneumonia in both groups (6.7% subjects in E-Bd and 4% subjects in Bd). In the E-Bd group, infection was reported in 16 subjects (21.3%); Grade 3-4 infections were reported in 11 subjects (14.7%). Similar results were reported for subjects in the Bd group (12 total subjects [16%]; Grade 3-4 in 9 subjects [12%]).

The most common Grade 3-4 event leading to discontinuation (i.e., in ≥ 2 subjects) in the E-Bd group was thrombocytopenia (2 subjects [2.7%]) and diarrhea (2 subjects [2.7%]), and in the Bd group was pneumonia (3 subjects [4%]), peripheral neuropathy (3 subjects [4%]), paraesthesia (3 subjects [4%]), and orthostatic hypotension (2 subjects [2.7%]).

Helsinki University Hospital Comprehensive Cancer Center Hematology
Clinical study protocol NMSG#24/15

The primary cause of death in subjects was disease progression (14 subjects [18.7%] in E-Bd group and 16 subjects [21.3%] in Bd group). There was 1 study drug-related death.

In the pooled data from all ongoing elotuzumab studies the death rate was 0.7% (6 patients) by the IB 10 Aug 2015, version 11.

Most common adverse reactions by the 11/2015 Prescribing information: 20% or higher: Fatigue, diarrhea, pyrexia, constipation, cough, peripheral neuropathy, nasopharyngitis, upper respiratory tract infection, decreased appetite and pneumonia

Table 4. Adverse drug reactions with elotuzumab

Adverse drug reactions in patients treated with elotuzumab in clinical studies			
System organ class	Preferred term	Overall frequency*	Grade 3-4 frequency

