Infections	Respiratory tract infection; Lung infection (pneumonia); Runny nose or nasal congestion	Sore throat; Bronchitis; Urinary tract infection; Inflammation of the nose and throat; Flu-like symptoms (influenza); Serious infection in the blood (sepsis); Viral infection		
Metabolism	Decreased appetite	Dehydration	Tumor lysis syndrome (TLS) (see "Conditions you need to look out	

Helsinki University Hospital Comprehensive Cancer Center Hematology
Clinical study protocol NMSG#24/15

Body System	Very Common (may affect more than 1 in 10 people)	Common (may affect up to 1 in 10 people)	Uncommon (may affect up to 1 in 100 people)	Rare (may affect up to 1 in 1000 people)
			for')	
Bone and Muscle	Back pain; Joint pain; Pain in limbs, hands or feet; Muscle spasms	Bone and muscle pain; Chest pain; Muscle weakness; Aching muscles		
Nervous System	Headache; Dizziness; Numbness, tingling; or decreased sensation in hands and/or feet			Posterior reversible encephalopathy syndrome (PRES) (see 'Conditions you need to look out for')
Psychiatric	Insomnia (difficulty sleeping),	Anxiety		
Kidney		Kidney problems, including decreased ability to make urine, increased creatinine in the blood, and kidney failure needing dialysis		
Skin		Rash; Itchy skin; Redness of the skin; Increased sweating		
Tests	Changes to blood tests (decreased blood levels of potassium, increased blood levels of sugar and/or creatinine)	Changes to blood tests (decreased blood levels of sodium, magnesium, protein, calcium or phosphate, increased blood levels of calcium, uric acid, potassium, bilirubin, or c-reactive protein)		
Immune System			Allergy to carfilzomib	

Helsinki University Hospital Comprehensive Cancer Center Hematology
Clinical study protocol NMSG#24/15

Body System	Very Common (may affect more than 1 in 10 people)	Common (may affect up to 1 in 10 people)	Uncommon (may affect up to 1 in 100 people)	Rare (may affect up to 1 in 1000 people)
Blood vessels	High blood pressure (hypertension)	Low blood pressure (hypotension); Blood clots in the veins	Stroke; Extremely high blood pressure (see 'Conditions you need to look out for')	

Important new safety information: In June, Amgen/Onyx has released new safety information on Carfilzomib based on the recently completed phase 3 trial. The information regards three types of adverse events:

Hypertension including hypertensive crises: Hypertensive crises have been reported in

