14. Participation in another interventional study within the 28 days before this study inclusion.
15. Patients refractory to carfilzomib or elotuzumab.
16. Primary plasma cell leukemia, systemic AL amyloidosis, Waldenström macroglobulinemia, rare IgM multiple myeloma, POEMS syndrome, myelodysplasia
17. Allogeneic or autologous stem cell transplantation planned
18. Participants receiving any other investigational agents or received within 60 days
19. Pleural effusions requiring thoracocentesis within the 14 days prior the inclusion.
20. Ascites requiring ascitespunction within the 14 days prior to inclusion.
21. Previous allogeneic transplantation
22. Uncontrolled hypertension or uncontrolled diabetes despite medication

- 23. Known hepatic cirrhosis
- 24. Severe autoimmune disease
- 25. Positive direct antiglobulin test (DAT), Coombs test

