- Grade 3 nausea, vomiting or diarrhea, unless persisting more than 3 days with adequate treatment of antiemetics or antidiarrheal agents
- Grade 3 dexamethasone-related hyperglycemia
- Grade 3 fatigue, unless persisting for > 14 days
- Alopecia

Table 9. Carfilzomib dosing guidelines for nonhematologic toxicity

Nonhematological toxicity	Recommended action
Renal dysfunction	
Serum creatinine equal to or greater than 2 x baseline, or CrCl < 15 ml/min, or decreases to ≤ 50% of baseline or need for dialysis	Withhold dose and continue monitoring the renal function If attributable to carfilzomib, resume when renal function has recovered to within 25% of baseline, start at 1 dose level reduction If not attributable to carfilzomib, dosing may be resumed at the discretion of the physician Patient will be withdrawn from study in case of permanent dialysis need
≥ grade 3 elevation in liver function tests	Withhold dose and resume at 1 dose reduction level when toxicity has recovered to baseline
Grade 3 infection	Withhold carfilzomib until infection resolves and resume at the same dose
Congestive heart disease	Any subject with symptoms of congestive heart failure, whether or not drug related, must have the dose held until return to baseline, after which treatment may continue at a reduced dose, or consider discontinuation of study protocol. If no recovery in 4 weeks, patient must be withdraw.
Left ventricular ejection fraction	
For resting LVEF < 40% or reduction of LVEF to < 55% if the drop is greater than 20% form baseline	Withhold until LVEF returns to > 40% or, if held due to a drop to < 55%, to within 15% of baseline and resume at 1 dose reduction.
Other grade 1 or 2 nonhematologic toxicity	Continue at the same dose
Any other drug-related nonhematologic toxicity ≥ grade 3	If attributable to carfilzomib, withhold dose Resume at 1 dose reduction when toxicity has resolved to grade 2 or less or to baseline If tolerated, the reduced dose may be escalated to the previous dose at the discretion of the physician
PRES: posterior reversible encephalopathy syndrome; headache, altered mental status,	Stop carfilzomib and study treatment and the patient is withdrawn from study. In visual or

Helsinki University Hospital Comprehensive Cancer Center Hematology
Clinical study protocol NMSG#24/15

seizures, visual loss, hypertension	neurological symptoms	neuroradiological imaging is recommended.
-------------------------------------	-----------------------	---

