9.3 DEMOGRAPHIC AND BASELINE CHARACTERISTICS

Baseline characteristics will include following parameters: age, sex, race, ECOG performance status, ISS stage (plasma albumin and serum-beta-2-microglobuline), paraprotein isotype, S- and U- paraprotein, S-FLC and ratio, hemoglobin, WBC, differential, platelet count, CRP, creatinine, calcium ionized, liver enzymes, LD, bone marrow morphology, bone marrow multiparameter flow cytometry, bone marrow cytogenetic analyses, FISH analyses t(4;14), +1q, cytogenetic del17p/p53 (if not previously diagnosed). Bone imaging will include skeletal ray or whole body low-dose CT, (MRI of spina and hip if clinically indicated).

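### No glucose test is scheduled although the protocol expects hyperglycaemia and its safety threshold would count it, so the grade ≥3 non-haematological rate may be understated.

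*Protocol*

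**What the plan says.** Three places in the protocol define the laboratory data, and none includes glucose.

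- Section 6.4, blood chemistry (screening, day 1 of each cycle and end of study in Table 1): creatinine and its clearance, liver enzymes, albumin, beta-2-microglobulin, LD, CRP, "Ionized calcium, sodium, potassium, phosphate", uric acid and the direct antiglobulin test.
- Table 1, the panel between day-1 visits: "Pvk+neut+tromb, K,Na,krea,alat, afos,bil (safety lab".
- Section 9.3, baseline characteristics, whose chemistry items include "creatinine, calcium ionized, liver enzymes, LD".

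Elsewhere the protocol treats hyperglycaemia as expected. Section 1.4.1.1 introduces the elotuzumab-bortezomib-dexamethasone data as relevant to the present study and reports grade 3-4 hyperglycaemia in 12%, against 5.3% without elotuzumab. Table 5 (1.4.2.2) puts "decreased blood levels of potassium, increased blood levels of sugar and/or creatinine" among the very common test changes with carfilzomib. Section 1.4.3 lists reduced glucose tolerance and hyperglycaemia for dexamethasone. Section 5.2.1 names "Grade 3 dexamethasone-related hyperglycemia" among conditions that do not require a carfilzomib reduction, and 4.2.2 excludes "Uncontrolled hypertension or uncontrolled diabetes despite medication".

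Section 9.2 sets the safety threshold at less than 70% grade ≥3 non-haematological adverse events, classified by CTCAE 4.0.

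**The concern.** Safety is part of the primary objective (2.1), and sections 4 and 9 make possible expansion depend on feasibility, safety and the expectations in 9.2. The threshold counts grade ≥3 non-haematological events. Hyperglycaemia is the most frequent single such term in the protocol's own reference regimen, and it can be present without symptoms.

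A site that follows Table 1 exactly would find it only if the patient became symptomatic or glucose was measured locally for another reason. Section 7.1 also tells staff not to ask about specific events. The count would then depend partly on local testing habits in a multicentre, single-arm trial with no control group to share the under-ascertainment. Missed events can only lower the observed rate. Hypokalaemia, at 5.3% the least frequent term in the same list, does have a scheduled test.

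**Working it through.** **Reproducing the 12%.** Section 1.4.1.1 gives counts with percentages for the elotuzumab-bortezomib-dexamethasone group: 16/0.213 = 75.1, 11/0.147 = 74.8 and 14/0.187 = 74.9, so n = 75. Then 9/75 = 12.0%, with exact (Clopper-Pearson) 95% CI 5.6% to 21.6%. The listed non-haematological grade 3-4 terms are hyperglycaemia 12%, diarrhoea 8%, peripheral neuropathy 8%, pneumonia 6.7% and hypokalaemia 5.3%. Grouped grade 3-4 infections are higher, at 17.3%, but that is a category and not one event.

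**Expected cases.** If 12% applied here, 0.12 × 40 = 4.8 patients.

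**Range of understatement.** The threshold is read as a share of patients, which is an assumption because 9.2 does not state the denominator.

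- Lower limit: 0 points, if routine care finds every case or every case also has another grade ≥3 non-haematological event.
- Upper limit: 12 points (4.8/40), if no case is found and none overlaps.
- Independence, none found, true overall rate p: the observed rate is q = 1 − (1 − p)/0.88. At p = 0.70, q = 1 − 0.30/0.88 = 0.659, a loss of 4.1 points.
- Independence, half found, p = 0.70: 1 − (0.30/0.88) × 0.94 = 0.680, a loss of about 2 points.

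**Effect on the threshold.** With N = 40, less than 70% means at most 27 patients with an event. Exact binomial probability of meeting it:

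| True rate | All found | Half found, independent | None found, independent | None found, no overlap |
|---|---|---|---|---|
| 60% | 87% | 93% | 97% | 99.6% |
| 70% | 42% | 53% | 64% | 92% |
| 75% | 18% | 25% | 34% | 77% |
| 80% | 4% | 7% | 10% | 53% |

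At a true 50%, the chance of at most 27 of 40 is already about 99%, so missed hyperglycaemia would change nothing.

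**Sensitivity to the 12%.** At the confidence limits, the no-overlap maximum would be 5.6 or 21.6 points instead of 12. At 5%, it would be 5 points (0.05 × 40 = 2 patients). Under independence at a true 70% the loss would then be 0.70 − (1 − 0.30/0.95) = 0.70 − 0.684 = 1.6 points.

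**The case against.** A reader might infer that hyperglycaemia is not measured at all and that the safety result is biased low by a definite amount. The documents do not support that.

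- **Other capture routes exist.** Section 7 records events that are observed, mentioned or spontaneously reported. Section 7.3 requires reporting of clinically significant laboratory results and of those leading to interruption or corrective therapy. Section 7.7 covers significant worsening in any safety assessment, required by the protocol or not. The 6.4 list is also not exhaustive: 4.2.1 needs AST for eligibility, and 6.4 does not name it. This stands, so the correct word is unscheduled. These routes still work only if somebody measures glucose or symptoms appear.
- **There is no internal contradiction.** Uncontrolled diabetes can be judged from the history. The 5.2.1 line says only that a carfilzomib reduction is not required, so no reduction is missed for want of a value. This stands.
- **The 12% comes from a bortezomib regimen.** Section 1.4.2.1 summarises weekly carfilzomib 70 mg/m² with dexamethasone, the backbone used here. Among the more frequent grade 3 events it names only acute renal failure and fatigue, each 5%. This stands as a reason to treat 12% as an assumption. Those data are preliminary and without elotuzumab, and not naming hyperglycaemia does not show that it was absent.
- **A minimum loss cannot be fixed.** Any floor above zero would need a detection rate and an overlap rate, and the protocol gives neither. This stands.
- **The decision may not be affected.** The listed reference terms sum to 12 + 8 + 8 + 6.7 + 5.3 = 40% even with no overlap (terms below 5% are not listed), well under 70%. The primary endpoint, overall response rate, is untouched. This stands and limits the weight of the point.

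**Conclusion.** The point holds as a gap in scheduled ascertainment. The protocol expects hyperglycaemia, would count grade ≥3 cases against its safety threshold, and schedules no test that would find asymptomatic ones. The direction of any error is certain: downward. The size is not known. It is 0 to 12 points if the 12% carries over, and about 4 points at a true 70% under independence with no detection. These figures assume that the threshold is a share of patients and that a bortezomib-based rate applies to this regimen.

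The safety conclusion could change only if the true rate lies near 70%, and nothing in the protocol shows that it does. The response endpoint is unaffected. This is a cheap improvement to safety data quality and does not make the safety result invalid. The laboratory schedule is protocol content, so the point is not one left to a statistical analysis plan.

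**What to change.** Add plasma glucose to the 6.4 chemistry list, so that it is measured at screening and on day 1 of each cycle. Add it to the existing safety-lab row of Table 1, on the days that row already covers. List baseline glucose in 9.3, and grade results by CTCAE as for the other laboratory values.

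The blood is already drawn at these visits, so the cost is one analyte per sample. The reported grade ≥3 rate may rise, which would reflect better ascertainment. No dose or treatment rule changes. If the sponsor prefers not to add the test, the protocol should state how hyperglycaemia is to be ascertained, and the report should say that it was not tested systematically.
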